### 11.2 Sample Size Considerations (RC-3)

For continuous outcomes we computed power using a variance correction (i.e., variance inflation factor) to take into account possible correlations of outcomes within cluster. All computations of required effective samples sizes (or corresponding power) were done using the PASS 2005 software. For binary outcomes, we used a specialized program for cluster randomization (a non-inferiority test comparing two proportions).

The primary outcome tooth pain was defined as change in pain (based on a 100-mm visual analogue pain scale (VAS), where higher is worse pain) from baseline to 1 year. We assume a mean difference of 0 between SDF and ART+FV, and consider non-inferiority to be within a margin (mean difference) of 8 between SDF and ART+FV arms; and based on prior literature also assume a common standard deviation of 25. Further, we assumed an average of 25 subjects recruited per site, an intraclass correlation (ICC) of 0.01 (based on prior studies and literature), and a 15% dropout rate (based on prior studies). The use of a 0.025 alpha-level one-sided t-test to test the null hypothesis of inferiority versus the alternative hypothesis of non-inferiority (as defined above), 11 sites per treatment group (corresponding to 275 subjects per treatment group or 550 total) will provide an estimated 89% power to conclude non-inferiority. Even if the ICC is higher (0.02), there will still be 83% power to detect non-inferiority.

A second primary outcome is arrest rate. Previous data show a high arrest rate (of around 90%) for ART + FV. We expect a similar arrest rate for SDF. For the power calculation we suppose the unit of analysis to be the person, and consider the binary outcome of 'arrest' defined as all lesions for an individual being arrested. We assume equal (person-level) arrest rates of 90% for the ART+FV and SDF groups, and consider non-inferiority to be within a margin (difference in arrest proportions for ART+FV versus SDF) of 0.09. With the same assumptions as before using a 0.025 alpha level one-sided z test, the targeted sample size of 275 subjects in 11 sites per treatment group will provide an estimated 85% power to conclude non-inferiority. For a higher ICC of 0.02, there will still about 80% power to detect non-inferiority.

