## 11.4 Final Analysis Plan (IR-1, RC-4)

Each primary outcome will be compared between the SDF and ART+FV groups. For tooth pain, a 95% confidence interval (CI) based on a t-test for the difference in mean responses (SDF minus ART+FV) will be computed. If this confidence interval lies within the interval  $(-\infty, 8)$  we may conclude 'non-inferiority' of SDF relative to ART+FV treatment. The confidence interval may secondarily be examined to assess possible superiority of one intervention over the other. For arrest rate, a 95% CI for the difference in rates (based on a z statistic) will be computed. If this confidence interval lies within the interval  $(-0.09, 1)$  we may conclude 'non-inferiority' of the SDF relative to ART+FV treatment. As above, possible superiority of one intervention over the other may also be assessed. For other outcomes, we will also compute 95% CI for differences in means (or proportions for binary outcomes). These secondary outcomes will be assessed in an exploratory manner for possibly superiority or inferiority based on appropriate margins.

We will seek to corroborate initial results using a generalized estimating equations (GEE) approach. For each outcome we will fit a GEE (marginal) model that includes a treatment indicator and prognostic variables (including sociodemographic variables, medical conditions, and oral health behaviors). Appropriate link functions (e.g., logit link for binary outcomes and identity link for continuous outcomes) will be specified and an exchangeable working correlation matrix used to allow for correlations within site. The arrest outcome will be analyzed as a binary outcome (as described in the sample size section), and secondarily as the number of arrested lesions assuming an appropriate distribution (e.g., negative binomial) and link function (e.g., log link). Robust t tests with correction for a small number of clusters will be used to test for treatment effects and corresponding 95% confidence intervals computed.

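### The plan does not say how the cluster-adjusted GEE result for caries arrest will be put on the risk-difference scale and judged against the -0.09 margin

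*Combined protocol and SAP*

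**What the plan says.** The margin is on the absolute scale. Section 11.2 puts it this way: "consider non-inferiority to be within a margin (difference in arrest proportions for ART+FV versus SDF) of 0.09". Section 11.4 uses the same scale for the decision: "For arrest rate, a 95% CI for the difference in rates (based on a z statistic) will be computed", and SDF is declared non-inferior if that interval lies within (-0.09, 1). Section 11.4 does not say that this interval is adjusted for site.

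The same section then turns to a GEE meant to support the initial results. It has an exchangeable working correlation within site, prognostic covariates, and robust t tests with a correction for few clusters. On the link it says: "Appropriate link functions (e.g., logit link for binary outcomes and identity link for continuous outcomes) will be specified". It promises tests of treatment effects and 95% confidence intervals. For arrest it gives no effect scale, no non-inferiority limit and no conversion to a risk difference. The sensitivity analyses listed later in 11.4 vary the covariance structure, the predictors and the distribution, but not the link or the effect scale.

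The two descriptions of the GEE's role differ. The main text of 11.4 has it corroborate. The Missing Data paragraph of 11.4 describes the primary analyses as GEE analyses of all available observations.

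**The concern.** Facilities are randomised (Section 5.4.1), so the analysis that allows for within-site correlation matters most for error control. For pain there is no difficulty: an identity-link GEE gives a mean difference, the scale on which the margin of 8 is set. For arrest, the treatment coefficient of a logit GEE is a log odds ratio, and its usual test is against an odds ratio of 1, not against the margin.

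Followed literally, the plan tests arrest against -0.09 only with an interval that has no stated cluster adjustment. The analysis with stated cluster adjustment is not tested against -0.09 at all. The choice of scale for the GEE would then be made after the data are seen, and, as shown below, that choice affects both the tolerated loss and the power.

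**Working it through.** **Inputs.** All are from Section 11.2. Test: "using a 0.025 alpha level one-sided z test". Rates: "We assume equal (person-level) arrest rates of 90% for the ART+FV and SDF groups". Margin: 0.09 on the difference. Size: "275 subjects per treatment group or 550 total", in 11 sites per arm, with "an average of 25 subjects recruited per site". ICC is 0.01, with 0.02 as the higher case, and dropout is 15%. The plan's result is that "the targeted sample size of 275 subjects in 11 sites per treatment group will provide an estimated 85% power to conclude non-inferiority"; for ICC 0.02 it gives about 80%.

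**Step 1: reproduce the plan's power.**
- Completers: 275 × 0.85 = 233.75 per arm, or 21.25 per site.
- Design effect = 1 + (21.25 - 1) × ICC = 1.2025 at ICC 0.01 and 1.405 at ICC 0.02.
- Effective n per arm = 233.75/1.2025 = 194.4, and 233.75/1.405 = 166.4.
- SE of the difference = √(2 × 0.9 × 0.1/n) = 0.0304 and 0.0329.
- Power = Φ(0.09/SE - 1.96) = 84.1% and 78.1%.

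The stated 85% and about 80% are reproduced within two points, on the risk-difference scale and with clustering allowed for.

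**Step 2: what is at stake if the deciding interval ignored clustering.** One-sided error at the margin = 1 - Φ(1.96/√design effect). This is 1 - Φ(1.787) = 3.7% at ICC 0.01 and 1 - Φ(1.654) = 4.9% at ICC 0.02, against a nominal 2.5%.

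**Step 3: the margin as an odds ratio.** With control (ART+FV) arrest rate p, OR = [(p - 0.09)/(1 - p + 0.09)] / [p/(1 - p)]. The last column holds the limit at the planning value of 0.474 and gives the risk difference it would tolerate. Only the 90% row is the plan's assumption; the other rates are scenarios.

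| ART+FV arrest rate | OR equal to -0.09 | Risk difference tolerated at OR 0.474 |
|---|---|---|
| 95% | 0.323 | -0.050 |
| 90% | 0.474 | -0.090 |
| 85% | 0.559 | -0.121 |
| 80% | 0.612 | -0.145 |
| 70% | 0.670 | -0.175 |

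For example, a lower limit of OR 0.52 means odds of 0.52 × 9 = 4.68, a rate of 0.824 and a difference of -0.076 at a 90% control rate, which is inside the margin. At an 80% control rate it means odds of 0.52 × 4 = 2.08, a rate of 0.675 and a difference of -0.125, which is outside. The planned GEE also adjusts for covariates, and adjusted odds ratios are non-collapsible, so this formula is illustrative and not a valid conversion for that model.

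**Step 4: the scale also changes power.** For a Wald test of the log odds ratio against 0.474, SE = √(2/(n × 0.9 × 0.1)) = 0.338 at n = 194.4, and the distance is ln(1/0.474) = 0.747. Power = Φ(0.747/0.338 - 1.96), about 60%. At ICC 0.02 it is about 53%. The risk-difference scale gives 84% and 78%.

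**Step 5: can the same GEE give a risk difference?** Yes. In simulation a logit GEE with exchangeable site correlation was standardised to a marginal risk difference, with a delta-method interval, bias-reduced robust SE and t on 20 df. The set-up was 22 equal sites of 21, beta-binomial site effects, one non-prognostic covariate and 500 runs per scenario.

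| ICC | Power, 90% in both arms | One-sided type I error, 90% v 81% |
|---|---|---|
| 0.01 | 78% | 1.4% |
| 0.02 | 73% | 2.4% |

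Monte Carlo error is about 2 points for power and 0.5 to 0.7 points for type I error. Much of the loss comes from the t reference: replacing z by t on 20 df in Step 1 already gives 80.3% and 74.0%.

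**The case against.** The strongest reply is that the decision rule has no scale mismatch. Margin, interval and acceptance region are all differences in proportions, and the main text of 11.4 gives the GEE only a supporting role. That is right as far as it goes, and the point should not be put as a faulty rule. It does not meet the Missing Data paragraph, which makes GEE primary, and a supporting analysis of a non-inferiority claim still needs a criterion for support.

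Four stronger readings are tempting, and the documents do not bear them out:
- A reader might infer that the arrest GEE is committed to a logit link. The logit is given as an example, so an identity link is not excluded.
- A reader might infer that a logit GEE cannot inform a risk-difference margin. Step 5 shows that it can; what is missing is the instruction to do it.
- A reader might infer that a non-significant odds ratio would be taken as non-inferiority. Section 11.4 defines non-inferiority only by an interval lying inside stated limits.
- A reader might infer that the z-based interval certainly ignores clustering, or that no other arrest analysis could allow for it. The plan is silent on the first, and the sample size does allow for clustering. On the second, the secondary repeated-measures analysis may add facility as a cluster level, with a mixed model as fallback. That is conditional and also has no stated route to the margin.

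**Conclusion.** The gap is real and limited. The plan does not state how the cluster-adjusted arrest result will be expressed as a risk difference and compared with -0.09, and it is inconsistent on whether that analysis is primary. The margin's odds-ratio equivalent runs from 0.47 at the planned 90% control rate to 0.61 at 80%, so no single odds-ratio limit can stand in for it.

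The error figures of 3.7% and 4.9% apply only if the z-based interval is computed without a cluster adjustment, and they rest on the plan's ICCs and 21.25 completers per site. All the calculations use the 22-site, 550-participant design to which the stated power applies. The added facilities and 40 extra participants were not modelled. This is a cheap improvement, not a flaw that invalidates the primary comparison.

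**What to change.** In Section 11.4, before arrest is compared between arms:

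1. State that the arrest GEE reports a marginal risk difference (SDF minus ART+FV), from a logit link with marginal standardisation or from an identity link.
2. Give it a 95% confidence interval from the small-sample-corrected robust variance with a t reference, naming the degrees of freedom.
3. Compare that interval with -0.09.
4. Reconcile the main text with the Missing Data paragraph on which analysis decides non-inferiority. If the z-based interval stays decisive, state how its standard error allows for site.

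The cost is a few sentences and one post-estimation step, with no new data. The price is somewhat lower power than stated: about 78% at ICC 0.01 and 73% at ICC 0.02 in the simulation, against 85% and about 80%.

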## 5.4 Treatment Assignment Procedures

### 5.4.1 Randomization Procedures (RQ-2)

Randomization is at the level of the cluster (housing facility) for logistical efficiency. This will greatly reduce the potential for error that could otherwise occur with people at the same site assigned to different treatments. Furthermore, keeping the same treatment at each site reduces chances of 'contamination' (i.e. participant discussing their treatment with others). Additionally, stratified cluster randomization will be used, i.e. a block (constrained) randomization approach in which balance over treatments is assured for 2 key cluster-level (stratification) variables, namely facility size (>100 versus ≤100 residents), and geographic location (Cuyahoga County vs other). The project statistician, [name] will generate the randomization scheme for the 22 + 4 additional housing facilities. While the randomization is at the housing level, the study objectives, interventions and primary outcomes all pertain to the individual level (RC-1).

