Secondarily, we will extend the above GEE approach to analyze the repeated (baseline, 26 and 52-week) measures for each outcome. The models for each outcome will include the same prognostic variables as before, as well as time and a time by treatment interaction. We will allow for correlations among the repeated measures, e.g., using a first-order autocorrelation structure. If a substantial within-facility correlation is found we may need to incorporate facility as a second cluster levels (within which person – the first cluster level – is nested). We will estimate and test (via a robust t-test) the interaction term to compare trends over time for the two interventions. If the use of two cluster levels is not found to be feasible in the GEE approach, we will consider a generalized mixed effects model approach.

**Causal Inference standards (CI-1, CI-2, CI-3, CI-4):** Our use of randomization and adjustment in regression models should be sufficient to provide causally interpretable intervention effect estimates; special causal inference techniques such as propensity score or instrumental variable methods often indicated for observational studies, will therefore not be necessary for our data analysis. We will avoid biases in causal inferences about the intended interventions by using an intent-to-treat approach, in which individuals are analyzed according to randomized groups without regard to (extent of) treatment actually received.

**Sensitivity Analyses IR-5:** We will check sensitivity of conclusions to model assumptions as well as methodological decisions such as outcome definition. In particular, for the arrest outcome, our primary analysis is based on a binary indicator of 'complete' arrest of all lesions for an individual. We will seek to corroborate results from this approach with an alternative approach analyzing

number of lesions arrested. For the GEE analyses, planned for all outcomes, sensitivity will be assessed in part by using alternative working covariance structures and alternative sets of predictors. For some outcomes, alternative distributions will be considered; for example, for number of arrested lesions, possible distributions include Poisson, negative binomial, zero-inflated Poisson (ZIP), and zero-inflated negative binomial (ZINB). Sensitivity to assumptions regarding missing data will also be investigated as described further below.

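### The secondary repeated-measures GEE clusters on person and adds facility only if its correlation looks substantial, so its treatment-by-time test is anti-conservative wherever facilities differ in change over time

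*Combined protocol and SAP*

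**What the plan says.** Section 5.4.1 fixes the unit of assignment: "Randomization is at the level of the cluster (housing facility) for logistical efficiency". Section 11.4 then describes two GEE analyses that treat that fact differently.

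- **52-week GEE.** Site correlation is handled unconditionally, with "an exchangeable working correlation matrix used to allow for correlations within site", and the robust t-tests carry a correction for few clusters.
- **Repeated-measures GEE (baseline, 26 and 52 weeks; introduced as secondary).** The default is correlation within person: "We will allow for correlations among the repeated measures, e.g., using a first-order autocorrelation structure". Facility is conditional: "If a substantial within-facility correlation is found we may need to incorporate facility as a second cluster levels". The text calls facility the level "within which person – the first cluster level – is nested". The test is of treatment by time: "We will estimate and test (via a robust t-test) the interaction term to compare trends over time for the two interventions". The fallback reads: "If the use of two cluster levels is not found to be feasible in the GEE approach, we will consider a generalized mixed effects model".

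The plan does not say what counts as a substantial correlation, how it would be assessed, or on which scale (level or change). The small-cluster correction is not restated for this model.

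Section 11.2 does not assume that the correlation is zero. It plans on "an intraclass correlation (ICC) of 0.01 (based on prior studies and literature", with 0.02 as a less favourable value, and defines the pain outcome as change from baseline to one year.

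**The concern.** A GEE robust variance is summed over the declared clusters and assumes that those clusters are independent. With person as the cluster, residents of one facility count as independent replicates of the treatment assignment, which they are not when the whole facility receives one arm. The sample size section pays for this with a design effect; the repeated-measures analysis may not.

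Making facility conditional on the data does not repair this. It lets a preliminary look with low power choose the variance estimator. Correlations of 0.01 to 0.02 are hard to detect with about 22 sites but large enough to change the standard error.

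At stake is a between-arm comparison of trends with intervals that are too narrow and too many false treatment-by-time findings. The analysis is secondary, but the heterogeneity paragraph of Section 11.4 says the primary hypothesis also covers the longitudinal effect, so readers will treat the result as evidence.

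**Working it through.** **Inputs (Section 11.2).** 275 recruited per arm in 11 sites, 25 per site, 15% dropout, ICC 0.01 or 0.02, one-sided alpha 0.025; pain margin 8 and SD 25; arrest 90% in both arms with margin 0.09.

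**1. Reproduce the plan's power.** Evaluable per site: m = 25 × 0.85 = 21.25. Evaluable per arm: 275 × 0.85 = 233.75. Design effect DE = 1 + (m − 1) × ICC; effective n per arm = 233.75 / DE.

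| ICC | DE | Effective n per arm | Pain power (stated) | Arrest power (stated) |
|---|---|---|---|---|
| 0.01 | 1 + 20.25 × 0.01 = 1.2025 | 194.4 | 88.4% (89%) | 84.1% (85%) |
| 0.02 | 1 + 20.25 × 0.02 = 1.405 | 166.4 | 83.1% (83%) | 78.1% (about 80%) |

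Pain power is Φ(8 / (25 × √(2/n)) − 1.96); arrest power is Φ(0.09 / √(2 × 0.09/n) − 1.96), where n is the effective n. All four figures agree within two percentage points, so these are in effect the plan's own inputs.

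**2. Error if facility is ignored.** A nominal two-sided 5% test whose variance omits DE has true error 2 × (1 − Φ(1.96/√DE)).

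- ICC of change 0.01: 1.96/√1.2025 = 1.787, error 7.4%; a 95% interval covers 92.6%.
- ICC of change 0.02: 1.96/√1.405 = 1.654, error 9.8%; coverage 90.2%.

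**3. Simulation checks (no true effect, 22 facilities × 21 residents, three waves, within-person AR(1) with correlation 0.5 assumed).** The first four columns use 20,000 replicates and test baseline-to-52-week change. The last column is a person-clustered GEE with exchangeable working correlation and 600 replicates. The pre-test column rests on an assumption: *substantial* is taken to mean a facility F-test at p < 0.05.

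| ICC of change | Person-level test | Facility-level t (20 df) | Pre-test brings facility in | Error under pre-test rule | Person-clustered GEE |
|---|---|---|---|---|---|
| 0.01 | 7.2% | 4.8% | 16% | 6.3% | 6.8% |
| 0.02 | 9.9% | 5.1% | 33% | 7.3% | 10.2% |

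With no facility correlation in change, the GEE gave 4.8%.

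**4. A facility effect constant over time.** With ICC 0.01 to 0.05 in level and none in change, the person-level test had 4.8% to 5.2% error. The effect subtracts out of the interaction.

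**5. Added sites.** The Protocol Summary and Table 1 give 22 plus 11 sites; Sections 4.2 and 5.4.1 still give 22 plus 4. Enrolment rises by 40 to 590. Equal site sizes are assumed.

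- 33 sites: m = 590 × 0.85 / 33 = 15.2; DE 1.14 and 1.28; error about 6.7% and 8.4%.
- 26 sites: m = 590 × 0.85 / 26 = 19.3; DE 1.18 and 1.37; error about 7.2% and 9.4%.

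**6. Cost in precision.** With facility as cluster and 20 df the multiplier is 2.086 instead of 1.96. Widening is (2.086/1.96) × √1.2025 = 1.17 and (2.086/1.96) × √1.405 = 1.26.

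**The case against.** The strongest objection concerns reach. A reader might infer that every treatment-by-time test in this plan exceeds its nominal error. The documents do not support that. Only facility correlation in change inflates the test, as step 4 shows. Section 11.2 ties the ICC to change for pain alone. For arrest, new decay and oral health quality of life, the size of any such correlation is unknown. There are reasons to expect some: under the COVID-19 procedures in Section 7, housing sites chose where exams took place, and on-site visits resumed only with their approval. For arrest, every participant enters with an active lesion, so there is no baseline facility difference to cancel a later one. These are reasons, not figures.

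A reader might also infer that facility would be left out of most analyses. The 16% to 33% entry rates depend on an F-test trigger that the plan never names. What stands is that no trigger is defined.

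It can further be said that the model extends the 52-week GEE and so inherits its site clustering. The sentence making facility an optional second level contradicts that reading. The mixed-model route gives no protection by default, since it is considered only if two cluster levels prove infeasible. Alternative working covariance structures, planned as sensitivity analyses, do not help while the sandwich is summed over persons.

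Finally, the analysis is secondary, and the stated non-inferiority rules use 52-week confidence intervals. That is correct and limits the weight of the point.

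**Conclusion.** The concern holds in a bounded form. In a facility-randomised trial, the plan lets an undefined look at the data decide whether the repeated-measures variance respects the unit of randomisation. For change in pain, on the plan's own ICC of 0.01 to 0.02, ignoring facility turns a nominal 5% test into one of about 7.4% to 9.8% with 22 sites, or about 6.7% to 8.4% if 590 participants are spread evenly over 33 sites. Under the assumed F-test trigger, the overall error is about 6% to 7%. For other outcomes the inflation depends on an ICC of change that the documents do not give, and it is nil if facility effects are stable over time.

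The inflation is moderate and confined to a secondary analysis. It does not undermine the 52-week non-inferiority rules, and nothing here should be read that way. The change should be made because the rule is wrong for the design and costs one sentence to correct.

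**What to change.** In Section 11.4, replace the conditional sentence on facility with:

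> In every repeated-measures GEE the independent cluster is the facility; the sandwich variance is summed over facilities, with the same small-cluster correction and t-test as in the 52-week GEE, whatever the estimated within-facility correlation.

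Because persons are nested in facilities, this variance covers within-person and within-facility correlation under any working structure.

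If a mixed model is used instead, specify person and facility random effects plus facility-by-time random effects, with small-sample degrees of freedom. Facility and person intercepts alone are not enough: a facility intercept also cancels from the interaction, so its standard error still omits facility variation in change. Fitted to data with an ICC of change of 0.02 and no effect (22 × 21, 1,680 fits), that model still had about 8% error.

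**Cost.** One sentence, a matching edit to the mixed-model fallback, and no new data. Intervals for this secondary analysis become about 17% (ICC 0.01) to 26% (ICC 0.02) wider than person-level intervals with 22 sites and 20 df, and somewhat less with more sites. The design effect alone would suggest 10% to 18%; the rest comes from the t multiplier.

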Missing Data. *(a) Methods to prevent and monitor missing data (MD-1, IR-7):* All questionnaires (using tablets) and dental assessment forms (using paper), will be managed in an electronic database (REDCap) by study staff. Weekly quality control checks will be run for outliers, entry errors, missing data, and potential data anomalies. Statistical analyses, summary and missing data reports will be generated by the study biostatistician ([name]) monthly during the study. *(b) Statistical Methods to Handle Missing Data and Account for Statistical Uncertainty Due to Missingness (MD-2):* The primary analyses, which use GEE based on all available observations, assume outcomes are missing completely at random (MCAR). As an initial assessment of missing data patterns, intervention groups (including by relevant subgroups and time point) will be compared with regard to missing outcome rates. We will test for a relationship between missingness and outcomes at early time points to evaluate the plausibility of the MCAR assumption. We will use multiple imputation methods (an established method) to help assure valid inferences. *(d) Plans to Record and Report Dropout and Missing Data (MD-3, IR-7):* The trial data will be managed using REDCap software, currently running at Case Western Reserve University (CWRU). REDCap is a secure web-based application providing an intuitive interface for validated data entry, audit trails for tracking data manipulation and export procedures, and automated export procedures for seamless data downloads to common statistical packages. Missing data reports will be generated weekly from REDCap for timely resolution and reporting purposes. *(e) Plans to Examine Sensitivity of Inferences to Missing Data Methods (MD-4):* As noted above, multiple imputation will be used to obtain valid inferences in the presence of data that are not missing completely at random. We will use predictive mean matching with an appropriate prediction model depending on the outcome (e.g. logistic regression for binary outcomes, linear regression for continuous and count outcomes). Alternative imputation models will be used as part of sensitivity analyses.

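### The deciding analyses use available cases under MCAR; multiple imputation is planned but not tied to the non-inferiority decision, and no missing-not-at-random check is named

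*Combined protocol and SAP*

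**What the plan says.** Section 11.4 speaks about the primary analysis in two places.

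- **Decision rule.** For pain: "For tooth pain, a 95% confidence interval (CI) based on a t-test for the difference in mean responses", with non-inferiority concluded if the interval lies below 8. For arrest: "For arrest rate, a 95% CI for the difference in rates (based on a z statistic) will be computed", with non-inferiority concluded if it lies above -0.09. GEE comes afterwards: "We will seek to corroborate initial results using a generalized estimating equations (GEE) approach", with "an exchangeable working correlation matrix used to allow for correlations within site". No imputation is mentioned in this text.
- **Missing Data paragraph.** "The primary analyses, which use GEE based on all available observations, assume outcomes are missing completely at random (MCAR"). The paragraph then plans to compare missing-outcome rates between arms, to test missingness against early outcomes, and to use multiple imputation. On the imputation model: "We will use predictive mean matching with an appropriate prediction model depending on the outcome", with the examples "e.g. logistic regression for binary outcomes, linear regression for continuous and count outcomes". It lists no predictors and does not mention facility. It adds that alternative imputation models will serve as sensitivity analyses.

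Elsewhere, Section 11.2 assumes "a 15% dropout rate (based on prior studies"). Section 3.2.1 has the primary outcomes measured at baseline, 26 and 52 weeks. Section 7.4 ends data collection for anyone who withdraws or moves out of the facility. The COVID-19 modifications in Section 4.2 report about 40 enrolled people who missed the 26-week visit (40/550 = 7.3% of the planned sample).

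**The concern.** In a non-inferiority trial, losing participants whose treatment has failed can pull the arms together and make a worse treatment look acceptable. MCAR rules this out by assumption, and the trial gives reason to doubt it: some losses come from withdrawal and moving out, and others from restrictions at the housing sites.

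The 26-week outcome, which is the best predictor of a missing 52-week outcome, is already collected. Neither the t/z intervals nor the 52-week GEE uses it. Multiple imputation could use it, but the plan does not say what happens if the imputed and available-case results fall on opposite sides of the margin, or if the MCAR check fails. The choice of headline result is then open after the data are seen. Nor does any named analysis tell the reader how much worse the missing SDF participants would have to be before the non-inferiority claim failed.

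**Working it through.** **1. Planned precision (Section 11.2).** Inputs: 275 per arm, 25 per site, 15% dropout, ICC 0.01 or 0.02, SD 25, arrest 90% in both arms, margins 8 and 0.09, one-sided alpha 0.025.

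- Observed n per arm = 275 x 0.85 = 233.75; mean observed cluster size = 25 x 0.85 = 21.25.
- Design effect = 1 + 20.25 x ICC, which is 1.2025 or 1.405. Effective n is 194.4 or 166.4.
- SE for pain = 25 x sqrt(2/n_eff) = 2.536 or 2.741. SE for arrest = sqrt(2 x 0.9 x 0.1/n_eff) = 0.0304 or 0.0329.
- Power = Phi(margin/SE - 1.96). Pain: 88.4% and 83.1% (plan: 89% and 83%). Arrest: 84.1% and 78.1% (plan: 85% and about 80%).

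The stated power is reproduced to within 2 points, so these SEs are a fair basis for what follows.

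**2. Bias when dropout depends on the 26-week outcome.** All rates in this step are assumptions. The same rule applies in both arms: 10% drop out if arrested at week 26 and 30% if not; week-52 arrest is 95% and 50% respectively. Let w be the proportion arrested at week 26.

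- True rate = 0.95w + 0.50(1 - w)
- Available-case rate = [0.9 x 0.95w + 0.7 x 0.50(1 - w)] / [0.9w + 0.7(1 - w)]

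| | w | Dropout | True | Available cases |
|---|---|---|---|---|
| SDF | 0.70 | 16% | 0.815 | 0.7035/0.84 = 0.8375 |
| ART+FV | 0.90 | 12% | 0.905 | 0.8045/0.88 = 0.9142 |
| Difference | | | -0.090 | -0.077 |

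The bias is +0.0133 in favour of SDF, or 15% of the 0.09 margin. It arises because SDF has more early failures to lose.

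Error at the margin: the SE of the available-case difference, with observed n of 231 and 242 and design effects based on 21 and 22 per site, is 0.0332 (ICC 0.01) or 0.0358 (ICC 0.02). One-sided error = Phi(-1.96 + 0.0133/SE) = 0.060 or 0.056, so about 6% instead of 2.5%.

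**3. How the bias varies.** The rule of step 2 is kept and only w changes.

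| w, SDF / ART+FV | True difference | Available cases | Bias |
|---|---|---|---|
| 0.70 / 0.90 | -0.090 | -0.077 | +0.013 |
| 0.80 / 0.889 | -0.040 | -0.033 | +0.007 |
| 0.90 / 0.90 | 0 | 0 | 0 |

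A second route is unequal dropout, where bias = (difference in dropout) x (outcome gap between missing and observed). With 20% dropout in SDF and 10% in ART+FV (assumed), an arrest gap of 0.1 to 0.3 gives 0.01 to 0.03 in favour of SDF (11% to 33% of the margin). A pain gap of 5 to 15 mm gives 0.5 to 1.5 mm (6% to 19% of the margin). With the dropout split reversed, the bias has the same size and works against SDF.

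**4. Tipping point.** Take an observed difference of 0, 15% missing in SDF and the SEs of step 1. Shifting only the imputed SDF values by delta moves the arm mean by 0.15 x delta, so delta = (margin - 1.96 x SE)/0.15.

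- ICC 0.01: pain (8 - 4.97)/0.15 = 20.2 mm; arrest (0.09 - 0.0596)/0.15 = 0.20.
- ICC 0.02: pain (8 - 5.37)/0.15 = 17.5 mm; arrest (0.09 - 0.0645)/0.15 = 0.17.

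**5. Facility in the imputation model, if it were left out.** With m = 25 and observed share r = 0.85, the ratio of the imputation variance to the true variance is [1/r + (m - 1) x ICC x r^2] / [1/r + (m - 1/r) x ICC]. Its square root, the SE ratio, is 0.977 at ICC 0.01 and 0.960 at ICC 0.02. Simulation (22 sites of 25, 20 imputations, 2,500 runs, normal-model imputation standing in for predictive mean matching) gave 0.971 and 0.949. Fixed site effects overshot: SE ratios of 1.12 and 1.09, with one-sided error of 0.014 to 0.016.

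**The case against.** The plan is not silent on missing data. It plans MCAR checks and multiple imputation, and it labels only the alternative imputation models as sensitivity analyses. It would be wrong to read imputation as firmly relegated to a back-up role; its status is simply not fixed. A GEE adjusted for prognostic variables also tolerates missingness that depends only on those variables. These points stand, but none ties the imputed result to the decision, and the covariates are baseline ones, so they do not cover dropout driven by the 26-week outcome.

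Section 11.4 also plans a repeated-measures GEE that uses the 26-week data. It is secondary, and an ordinary GEE does not become valid under missing at random by including earlier visits. The mixed model, which could be, is considered only if two cluster levels prove infeasible in the GEE.

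Two stronger readings are tempting. One is that the imputation is single-level, without facility, so that its interval is too narrow. The text gives logistic and linear regression as examples and neither includes nor excludes facility. The narrowing is conditional on omission and is only about 2% to 5% at the planned ICCs. The other is to quote the bias within one arm as the bias of the trial. Non-inferiority rests on the difference, and part or all of a one-arm bias cancels.

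Finally, a tipping point near 20 mm or 20 points suggests robustness rather than fragility. That is fair for an observed difference of 0 at planned precision. The shift shrinks as the observed difference moves towards the margin, and the plan does not commit to reporting it.

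**Conclusion.** The concern holds in this form: whichever of the two analyses in Section 11.4 is taken as primary, it uses available cases; multiple imputation is not linked to the decision rule; the MCAR check leads nowhere; and no missing-not-at-random analysis is named. The inconsistency over which analysis is primary is part of the problem, because it leaves no fixed place for imputation to attach.

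The bias is conditional. It favours SDF if dropout follows early failure and SDF fails more often, or if SDF loses more participants who are doing worse. In the illustration it is 1.3 points of arrest, or 15% of the margin, and takes one-sided error to about 6%. It is zero if the arms have the same arrest rates and dropout. These rates are assumed, and the documents give no 26-week arrest or arm-specific dropout figures. A reader might infer that the trial's result is biased towards SDF; the documents show only that the plan does not protect against it.

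On facility, the defect is underspecification, with a small effect if facility is omitted.

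**What to change.** 1. Name one deciding analysis for each primary outcome and make the two parts of Section 11.4 agree.
2. Base it on multiple imputation of the 52-week outcome, done separately by arm, from the baseline and 26-week outcomes, lesion count and the prognostic variables, with a random facility effect. Do not use fixed site effects, which overshoot. State how a missing 26-week value is handled, since about 40 people missed that visit and the correction works only as far as 26-week status is known or well predicted.
3. Keep the available-case analysis as a sensitivity check, and say that the imputed result stands whatever the MCAR check shows.
4. Add a tipping-point run that worsens only the imputed SDF values until the confidence interval crosses 8 (pain) or -0.09 (arrest), and report that shift for each outcome.

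The cost is SAP wording and programming. No new data are needed. The confidence interval would be slightly wider than under imputation that ignored facility.
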